2.0	17-JUL-2020	
 Update protocol version number and date on title page, footer, Protocol Approval Page and Investigator Protocol Signature Page. Revise List of Abbreviations to add BMSi. Revise section 1 Study Summary including 1.1 Schedule of Events to reflect changes made in the body of the protocol and add the name and address of the Investigator and CRO. Revise section 3.7 Device Traceability to include detailed information on tip assembly labeling and device accountability. Revise section 3.8 Supply and Accountability of Investigational Devices to indicate that device storage instructions are documented in the User Guide. Revise section 4.0 Benefit-Risk Analysis to correct the number of peer reviewed articles from 41 to 40. Revise section 4.2 Risk Mitigation to correct the name of the product documentation and add a bullet to indicate that subject IDs will be used to mitigate risk. Revise section 4.3 Anticipated Benefits to make it clear that there are no anticipated benefits to study subjects Revise section 4.4 Risk to Benefit Ratio to indicate that the Investigator will be trained on the protocol. Revise section 5.2 Secondary Objectives to indicate that safety events will be characterized. Revise section 6.1 Study Duration to specify that AEs will be followed until no further resolution is expected. Revise section 7.4 Exclusion Criteria to add clarity to existing exclusions, specify exactly how conditions such as allergies and infections will be determined and documented, specify that only topical antibiotics used at the procedure site are exclusionary, specify that only infections at the procedure site are exclusionary and exclude patients with needle phobia and additional conditions listed in exclusion criteria #14 Revise section 7.6 Informed Consent to refer to IRB guidelines. Revise section 7.8 Screen Failures to indicate that Screen Failures will be captured on a log and re-screens require sponsor approval. Revise sections 7.10 Subject Enrollment and 7.11 Treated Subjects to clarify when patients are considered enrolled and treated and that treated subjects will be followed for 30 days. Revise section 8 Study Visit Procedures to clarify steps and order, list vitals to be captured, allow for screening procedures to be completed over a seven day period, and specify that

Clinical Study Protocol

		
follow ups may be in person or over video (telehealth) with body temperature measurements to help detect possible infections.
 
 Revise section 9 Description of Study Procedures to clarify how the medical history will be captured, specify the vitals to be captured and document how pregnancy will be evaluated and tested. Revise section 10.2 Subject Withdrawals to clarify that patients who withdraw consent prior to treatment will be considered screen failures. Revise section 14.1 Definitions to add the definition of a device deficiency and revise the definition of an SAE to match FDA's definition, Revise section 14.2.2 Relationship to provide detail on how AE relationship to the investigational device will be determined. Revise section 14.3 AE Reporting Procedures to clarify when AE collection begins and requirements for AE reporting, study termination and updating AE status. Revise section 14.4 Treatment of AEs to clarify that AEs will be followed until resolved or no further improvement is expected. Revise section 14.5 Clinical Events Committee to clarify the role of the CEC. Revise section 15 Study Monitoring to include the name and address of the CRO. Revise section 18 Regulatory Considerations and Ethical Review to list all accurate regulatory requirements. Revise section 18.4 Insurance to clarify who is insured and what they are insured for. Revise section 19.1 Data Handling and Record Keeping to clarify roles and responsibilities. Revise section 19.2 Record Keeping to include accurate regulatory requirements for retention of study records. Revise section 19.4 Publication and Data Sharing Policy to indicate that the study will be registered on clinicaltrials.gov and results posted. Minor administrative changes involving grammar, wordsmithing, punctuation, page numbers and other editorial changes have been made throughout the document. All are clearly identified in the track-changes version of the amendment.
3.0	08-SEP-2020	
 Revise sections 1, 1.1, 7.4, 8 and 9 to add x-rays for screening and adverse event evaluation. Revise section 7.9 to clarify that subject IDs are not generated by the investigational device Revise section 7.10 and 14.3.1 to clarify the point of enrollment

1. STUDY SUMMARY

Study Full Title	A Single-arm, Open Label Clinical Study to Collect Safety Data on the OsteoProbe System when used as a Measurement Tool
Study Sponsor	Active Life Scientific, Inc.
Study Number	OP2020
Protocol Date	17-JUL-2020
STUDY OVERVIEW	
Study Design	Prospective, Single Center, Open Label Clinical Study
Purpose	Collect safety data associated with the use of the OsteoProbe System.
Expected Study Duration	
The study is expected to take approximately 3 months from first subject enrolled to the last follow-up visit.
 
 • 2 months enrollment period (estimation) • 1 month follow-up
Evaluation Schedule	
Each subject will be evaluated at:
 
 • Screening/Procedure • 1-Day (+2 days) • 7-Day ((±3 days) • 30-Day (±10 days)
ELIGIBILITY CRITERIA	
Intended Subject Population	A total of 40 subjects will be enrolled at 1 site.
Main Inclusion Criteria	
In order to be eligible to participate in this study, subjects must meet all of the following inclusion criteria:
 
 1. Be greater than or equal to 22 years of age; 2. Be able to give voluntary, written informed consent to participate and have signed an Informed Consent Form specific to this study 3. If female and of child-bearing potential, must have a negative pregnancy status.
Main Exclusion Criteria	
Subjects who meet any of the following criteria will be excluded from participating in this study:
 
 1. Active skin infection at the procedure site as identified during a SOC physical examination. 2. Subject-reported or known systemic infection; 3. Subject-reported or known allergy to local anesthetic; 4. Subject-reported or known allergy to stainless steel or nickel materials; 5. Subject-reported or known current use of systemic antibiotics, or topical antibiotics administered to the procedure site;

Clinical Study Protocol

	
 6. Subject-reported or known history of needle phobia; 7. Significant soft tissue at the procedure site which would preclude use of the OsteoProbe in the judgement of the Investigator; 8. Known instance of hardware in the tibia that is intended to be measured based on radiographic imaging; 9. Known instance of a previous or current fracture in the tibia that is intended to be measured based on radiographic imaging; 10. Are known to be actively participating or known to have participated in another clinical investigation for which they received an investigational product (including but not limited to a drug or vaccine) within the last 90 days, or reports that they intend to participate in another clinical investigation during the course of the study; 11. Are known to be currently abusing drugs or alcohol or have a known history of the same within the last 12 months; 12. Have any known or subject reported mental or psychological disorders that, in the judgement of the Investigator, would impair their ability to accurately complete the NRS Pain Score surveys; 13. Are currently a prisoner; 14. Have a condition which, in the judgement of the Investigator, would preclude adequate evaluation of the device's safety and performance. Conditions include but are not limited to: 
 a) Regional or systemic pain syndromes b) Radicular pain syndromes c) Chronic or intermittent leg pain d) Migraine headaches
STUDY ENDPOINTS	
Primary Endpoint	The incidence of device-related serious adverse events (SAEs) in subjects evaluated with the OsteoProbe System.
Secondary Endpoints	
The secondary endpoints of this study, following evaluation with the OsteoProbe System, are:
 
 1. NRS Pain scores at Procedure, 1-day, 7-day and 30-day follow up visits; 2. BMSi scores after the OsteoProbe procedure; 3. Adverse event rates through Day 30; 4. Device-related adverse events through Day 30; 5. Serious adverse events through Day 30; and 6. Unanticipated adverse device effects (UADE) through Day 30.
STATISTICAL CONSIDERATIONS	
Sample Size	40 IDE Subjects

Clinical Study Protocol

	
A literature review was performed by the Sponsor who identified six studies with clinically relevant data to serve as an informative prior. These six studies contain 215 subjects with zero subjects experiencing device-related serious adverse events. Given there is no variability between these studies, the data are pooled together and collectively constitute the informative prior. The informative prior was constructed as Jeffries prior plus the data from the literature, that is, Beta(.5 + data, .5 + data).
 
When there are zero device-related SAEs in 40 prospective subjects, the posterior probability will be .9765 and the device will have been shown to meet the performance goal. Therefore, only if there are zero device-related SAE's will the alternative hypothesis be accepted.

Statistical Plan
	
The primary hypothesis is that the probability of experiencing device-related Serious Adverse Events (SAE) for subjects treated with the investigational device is smaller than the performance goal of 1%. Formally, the hypothesis to be tested is:
 
H_0: The expected proportion of subjects with device-related SAE up to Day 30 (p_T) is greater than or equal to the performance goal (PG) of 1.0%.
 
H_A: The expected proportion of subjects with device-related SAE up to Day 30 (p_T) is less than the performance goal (PG) of 1.0%.
 
These hypotheses may be symbolically represented as:
 $H_0: p_T \geq PG = 1.0\%$ $H_A: p_T < PG = 1.0\%$ 
Where p_T is the device-related SAE rate for subjects treated with the investigational device.
 
If the Bayesian Posterior Probability that $p_T < PG$ is greater than or equal to .975, the alternative hypothesis will be accepted, and it will be concluded that the device meets the performance goal.

STUDY MANAGEMENT	

Principal Investigator
	
[name] MD Meridian Clinical Research, LLC, [name]

Clinical Research Organization (CRO)
	
MCRA, LLC [name]

1.1 SCHEDULE OF EVENTS

Activity	Visit 1 Screening/ Procedure ¹	Visit 2 1-Day ^{2,3} (+ 2 days)	Visit 3 7-Day ^{2,3} (±3 days)	Visit 4 30-Day ² (±10 days)	Unscheduled
Informed Consent	X	-	-	-	-
Inclusion/Exclusion Criteria Review	X	-	-	-	-
Demographics	X	-	-	-	-
Medical History	X	-	-	-	-
Physical Examination (including vitals)	X	-	-	-	-
X-Rays (AP & Lateral)	X	-	-	-	-
Pregnancy Evaluation/Test ⁴	X	-	-	-	-
OsteoProbe Test Procedure	X	-	-	-	-
NRS Pain Score	X ⁵	X	X	X	X
Record BMSi Score	X	-	-	-	-
Body Temperature		X	X	X	X
Record/Review Concomitant Medications	X	X	X	X	X
Record/Review Adverse Events	X ⁶	X ⁶	X ⁶	X ⁶	X ⁶
Record/Review Device Deficiencies	X	-	-	-	-
Work status	X	X	X	X	X

¹ The Screening/Procedure visit may take place over multiple days, but the OsteoProbe procedure must be completed within 7 days of signing the ICF.

² To be conducted as telehealth visits with video interviews; option of in-person visits is acceptable if that is preferred by a subject or the Investigator.

³ Measured from the date of the OsteoProbe procedure.

⁴ Female subjects of child-bearing potential only. Negative pregnancy status can be based on self-reported sexual history and contraception use. An in-clinic test must be performed using urine dipstick when the subject thinks there is a potential that they might be pregnant.

⁵ The NRS Survey must be completed once prior to the OsteoProbe procedure (baseline) and again following completion of the procedure.

⁶ X-rays will be ordered by the Investigator to evaluate any adverse event that may be related to a potential tibial fracture based on clinical exam and/or adverse event details provided by the subject.

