5.2 SECONDARY OBJECTIVES

Obtain information on pain regarding the procedure and characterize all safety events.

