6.2 TREATMENT/CONTROL GROUP

The study will be a single arm study with no control group.

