6.4 SECONDARY ENDPOINTS

The secondary endpoints of this study, following evaluation with the OsteoProbe System, are:

1. NRS Pain scores at Procedure, 1-day, 7-day and 30-day follow up visits;
2. BMSi scores after the OsteoProbe procedure;
3. Adverse event rates through Day 30;
4. Device-related adverse events through Day 30;
5. Serious adverse events through Day 30; and
6. Unanticipated adverse device effects (UADE) through Day 30.

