8. STUDY VISIT PROCEDURES

8.1 VISIT 1: SCREENING/PROCEDURE VISIT

Note: The Screening/Procedure visit may take place over multiple days, but the OsteoProbe procedure must be completed within 7 days of signing the ICF.

Upon successful documentation of informed consent, the subject will be screened to confirm subject eligibility. The screening will include a documentation of demographics, medical history, physical exam with vitals (temperature, blood pressure, pulse and respiratory rate), x-rays to rule out tibial fractures or implants, pregnancy evaluation (for women of childbearing potential only), work status, and concomitant medications.

Upon successful confirmation of subject eligibility, the subject will undergo the following:

Baseline NRS Survey

- The subject will complete a baseline Numerical Rating Scale (NRS) Survey right before initiating the OsteoProbe test procedure

OsteoProbe Test Procedure

- The Investigator will clean the test site and apply a local anesthetic agent prior to performing the OsteoProbe procedure, as outlined in the Procedure Guide, with the assigned device. The Investigator will note the anesthetic agent used, time of delivery and the volume administered in the subject's study records.
- The procedure start time will be recorded as the time of first insertion of the Tip to the bone surface
- The procedure stop time will be recorded as the time the Tip is removed from the skin following the final indentation
- The Investigator will consider the procedure to be successful once the OsteoProbe software displays the BMSi
- If the Investigator cannot complete the procedure for any reason, they should stop the use of the device on this subject and treat the subject per SOC

Post-Procedure (< 60 Minutes)

- The Investigator or delegate will apply a dressing to the test site per SOC
- The Investigator or delegate will record the BMSi Score
- The subject will complete the post-procedure Numerical Rating Scale (NRS) Survey—*this pain survey must be administered prior to performing any adverse event or device deficiency evaluations to prevent information from these assessments biasing the subject's responses.*
- The Investigator or delegate will record adverse events and device deficiencies, if applicable
- The Investigator or delegate will review the suggested post-procedure regimen with the subject per the User Manual
- The Investigator or delegate will perform a review of concomitant medications with the subject

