18.6 SECONDARY EFFECTIVENESS ENDPOINTS

The secondary endpoints of this study, following evaluation with the OsteoProbe System, are:

- Follow-up NRS Pain scores take at Procedure, 1-day, and 7-day follow up visits
- BMSi scores at Procedure
- Adverse event through day 30.
- All device-related adverse events through day 30.
- Serious adverse events through day 30; and
- Unanticipated adverse device effects (UADE) through day 30.

Secondary endpoints are described in the Clinical Protocol. Continuous variables will be described by the number of observations, the number of missing observations, means, standard deviations, medians,

Clinical Study Protocol

minimums, and maximum. Responder variables will be described by the number of observations, the number of missing observations, and percentages. Secondary endpoints may be further described through credible intervals or other posterior distribution summaries.

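### The protocol requires a baseline NRS pain score, but the SAP gives it no stated role; change from baseline should be tabulated beside the raw follow-up scores

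*Combined protocol and SAP*

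**What the plan says.** - **Collection.** Two scores are required at Visit 1 (section 1.1, footnote 5): "The NRS Survey must be completed once prior to the OsteoProbe procedure (baseline) and again following completion of the procedure". Section 8.1 fixes the timing of the first: "The subject will complete a baseline Numerical Rating Scale (NRS) Survey right before initiating the OsteoProbe test procedure". Further scores are taken at Day 1, Day 7 and Day 30 (sections 1.1 and 8.2 to 8.4).
- **Objective.** Section 5.2: "Obtain information on pain regarding the procedure and characterize all safety events".
- **Comparator.** Section 6.2: "The study will be a single arm study with no control group".
- **Endpoint.** Section 6.4 lists "NRS Pain scores at Procedure, 1-day, 7-day and 30-day follow up visits", under a lead-in that places the secondary endpoints after use of the device. SAP section 18.6 is narrower: "Follow-up NRS Pain scores take at Procedure, 1-day, and 7-day follow up visits".
- **Summary.** Section 18.6: "Continuous variables will be described by the number of observations, the number of missing observations, means, standard deviations, medians", followed by the minimum and maximum. It adds: "Secondary endpoints may be further described through credible intervals or other posterior distribution summaries". Section 18.5 rules out imputation for these endpoints.

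No section defines a change score, a paired summary or a baseline adjustment for the NRS. Section 18.8 stratifies by age category, sex and site only.

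**The concern.** The objective is pain connected with the procedure. With one arm, each subject's own pre-procedure score is the only comparator. It is collected from everyone and then has no stated use.

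Baseline pain cannot be taken as zero. Exclusion 14 (section 7.4) depends on the Investigator's judgement and sets no NRS ceiling. Subjects are recruited from ordinary patients (section 7.1). Section 13 has current pain medication of any kind recorded, and section 8.1 starts that record at screening. Section 9 does not restrict the NRS to the tibia, although the form itself is not in the documents.

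What is at stake is how clearly the pain results can be read. A Day 7 score of 4 may be unchanged from before the procedure or a rise from 0, and the planned table treats the two alike.

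**Working it through.** **1. The plan's own figure.** There is none for the NRS. The only design figure is the posterior probability of .9765 in section 18.2. A Jeffreys Beta(0.5, 0.5), plus 0 events in 215 prior subjects and 0 in 40 trial subjects, gives Beta(0.5, 0.5 + 215 + 40) = Beta(0.5, 255.5). P(p < 0.01) = 0.97649, which agrees. With one event in 40 it is 0.8368, below .975, so the zero-event rule also holds. No NRS quantity enters, so this point cannot alter the primary result.

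**2. Raw score against change.** For subjects with both scores, change = follow-up − baseline. Hence mean(follow-up) − mean(change) = mean(baseline), exactly.

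**3. Size, on assumed inputs.** The documents give no baseline mean or prevalence of pain. Suppose a share *s* of subjects has unrelated, steady pain at level *L*, the rest score 0, and the procedure has no effect. The raw follow-up mean is then *s* × *L*:
- *s* = 5% (2 of 40), *L* = 2: 0.05 × 2 = 0.1 points
- *s* = 20% (8 of 40), *L* = 4: 0.20 × 4 = 0.8 points

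The mean change is 0 in both cases.

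**4. What the planned table can miss.** Take 40 subjects, 39 scoring 0 throughout. In case A the remaining subject goes from 0 to 4. In case B that subject is at 4 before and after.

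| Statistic | Case A | Case B |
|---|---|---|
| Raw follow-up mean | 4/40 = 0.1 | 4/40 = 0.1 |
| Raw median; minimum; maximum | 0; 0; 4 | 0; 0; 4 |
| Mean change | 4/40 = 0.1 | 0 |
| Subjects with an increase | 1 | 0 |

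The follow-up scores are the same set of numbers, so every statistic in 18.6 agrees between the cases. Only the last two rows differ.

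**5. Precision.** If baseline and follow-up have equal variances and correlation *r*, SD(change)/SD(raw) = √(2(1 − *r*)). This gives 0.45 at *r* = 0.9, 0.77 at 0.7, 1.0 at 0.5 and 1.18 at 0.3. With n = 40 and an assumed SD of 1.5 to 2.0, the 95% half-width is 0.48 to 0.64 for a raw mean. For a mean change it is 0.30 to 0.76 over *r* from 0.8 to 0.3. The equal-variance condition may fail: if nearly all baselines are 0, the ratio moves towards 1.

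**The case against.** **A reader might infer that pre-existing and procedure pain cannot be separated in this trial.** The documents do not support that. The baseline score is mandatory, so the separation can be made from the data. Only the planned table lacks it.

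**The baseline may already be covered.** Section 6.4 lists scores at the procedure, and the Visit 1 NRS entry in section 1.1 covers both the score before and the score after. On that reading the baseline would be tabulated. Against it, 18.6 speaks of follow-up scores and 6.4 of endpoints after use of the device. Even on the generous reading no change is defined. The difference of two tabulated means equals the mean change only if the same subjects contribute to both, and it never gives the number of subjects who rose.

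**A reader might infer that raw means charge unrelated pain to the device.** They do not. Attribution runs through adverse events: a pre-existing condition counts only if it worsens (14.3.1), each event is graded for relationship (14.2.2), an independent committee adjudicates all events (14.5), and device-related events are listed (18.7). This stands and lowers the stakes. It does not supply a scaled measure of change.

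**Screening removes much of the relevant pain.** Exclusion 14 names leg pain, radicular pain, pain syndromes and migraine, and exclusion 9 removes fracture of the measured tibia. This also stands: baseline pain should be reduced, though nothing ensures that it is zero.

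**The maximum would show a large rise.** In part. A high score would be visible, but step 4 shows that the maximum does not say whether the score is new.

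**Change scores can be less precise.** True at low correlation (step 5). The case for them is relevance to the objective, so they belong beside the raw scores and not in their place. Raw levels do give some of the information that section 5.2 asks for.

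**Conclusion.** The point holds in a limited form. The SAP gives the required baseline NRS no stated role, and in a single-arm study the planned pain table therefore does not tell pre-existing pain from a rise after the procedure.

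The raw mean differs from the mean change by exactly the mean baseline score. How large that is cannot be known from the documents. The range of 0.1 to 0.8 points rests entirely on the assumption of 5 to 20% of subjects with steady unrelated pain at NRS 2 to 4. The precision figures rest on assumed SDs and correlations and on equal variances.

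The endpoint is secondary, descriptive and unpowered, and nothing here touches the test of device-related serious adverse events. Severity is low; this is a free improvement.

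**What to change.** In SAP section 18.6, beside the raw scores:
- Tabulate the baseline NRS.
- Tabulate within-subject change from baseline at post-procedure, Day 1, Day 7 and Day 30: n, mean, SD, median, range and a 95% interval, in subjects with both scores, since 18.5 excludes imputation.
- Give the number of subjects with any increase at each of these times.

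Two details belong in the same edit:
- **Which NRS item.** Section 9 describes a composite of best, worst and current pain over 24 hours. The post-procedure survey falls within 60 minutes of the procedure (section 8.1), so its 24-hour recall would largely overlap that of the baseline survey. If the composite is used, base the immediate post-procedure change on the current-pain item, and say so.
- **Day 30.** Sections 1 and 6.4 list the Day 30 NRS and 18.6 omits it. Reconcile them.

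The cost is a few lines in the SAP and one extra table. No new data or visits are needed, and the sample size and the primary analysis do not change. Stating the summary in advance also avoids a later choice among pain summaries in an open-label study.
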